4.0 Treatment Plan

Prior to randomization, eligible patients will have received 4-6 cycles of induction chemotherapy, erlotinib or afatinib (for patients with known EGFR mutations) or crizotinib (for patients with known EML4-ALK fusion) without evidence of RECIST progression. They will be registered and then randomized in a 1:1 fashion to either immediate or no/delayed LCT. All patients will be followed until progression of disease is documented or two years after randomization, whichever comes first. Patients with metastases involving the brain or spinal cord, or metastatic lesions causing symptoms requiring palliation (e.g., bone, soft tissue) may be treated with surgery or radiotherapy prior to the completion of induction chemotherapy (randomization).

The following imaging studies are suggested after first-line therapy to assess the number of sites: 1) imaging of the brain with either a magnetic resonance imaging (MRI) scan (preferred) or a CT scan of the brain with contrast, and 2) systemic imaging with a positron emission tomography/computed tomography (PET/CT) scan or a CT scan of the chest/abdomen/pelvis with contrast. Other studies, such as a bone scan, and aspiration of pleural fluid, are at the treating physician's discretion.

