4.2.3.6 Dose Calculation

Doses are to be calculated with CT based heterogeneity corrections, i.e. corrections are made for density differences between air spaces, lungs, water-density, or bone tissue.

5. Symptom Assessment during Protocol Treatment

A) As noted below in “Evaluation of Outcomes of Interest,” patients will be evaluated in the clinic for toxicity at follow-up visits every 8 +/- 2 weeks until 1 year, and then less frequently thereafter. Concordant with these clinic visits, the research team will capture toxicities in our toxicity log that meet the following criteria, per institutional policy: a) severe, defined as CTCAE v4.0 Grade 3 or higher, 2) unexpected, or 3) unanticipated. In addition, we will ensure that all relevant toxicities (severe, unexpected, or unanticipated) are documented appropriately in the medical record.

B) *Multiple-symptom assessment tool (optional)*. Symptoms will be measured by the Lung Cancer module of the MDASI²⁴. The MDASI is a multiple-symptom measure of cancer-related symptoms²⁵ that is sensitive to disease and treatment changes in lung cancer. This instrument is brief, easily understood, and validated in the lung cancer population. Patients rate the intensity of physical, affective, and cognitive symptoms on 0–10 numeric scales, ranging from “not present” to “as bad as you can imagine.” Patients also rate the amount of interference with daily activities caused by symptoms on 0–10 numeric scales, ranging from “did not interfere” to “interfered completely.” The MDASI-LC has 3 additional items known to be important in assessing patients with MM or MM therapies (constipation, coughing, sore throat). The MDASI-LC takes less than 5 minutes to complete. It can be completed at home using the web or an interactive voice response-computer system that calls the patient to have them rate their symptoms and symptom interference²⁶. Symptom severity and interference over time will be a secondary endpoint. The MDASI is included in Appendix C, and this data will be collected from each patient at each follow-up visit as described in the *Evaluation of Outcomes of Interest* section (every 6-8 weeks for the first year).

6. Optional Procedures after Induction Chemotherapy

A) Tissue specimen collection for biomarker analysis:

[figure not shown]

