7.4 Design

Design Assumptions:

Primary endpoint	Progression-free survival (PFS)
Null hypothesis	Median PFS equals to 4 months in both groups
Alternative hypothesis	Median PFS equals to 4 months in the delayed/no LCT group and equals to 7 months in the immediate LCT group.
Associated hazard ratio	0.57 = 75% improvement in median PFS
Type I error	10%
Type II error	10%
Accrual rate	2-3 patients/month
Follow-up	9 months

A design with one-sided 10% type I error and 90% power would require an expected number of progression events of 87 under the alternative hypothesis to detect 75% improvement in median PFS. Given these assumptions, this design would require 94 patients *randomized* over 37.6 months with additional 9 months of follow-up. One interim analysis will be performed to allow for the early termination of the trial in light of evidence that the LCT arm is superior to the no LCT arm or there is no difference between the two treatment arms. In order to provide an overall significance level of 0.05 for the study, the interim analysis will use a Lan-DeMets monitoring boundary with an O'Brien-Fleming stopping rule (East 5.4.2.0, Cytel 2011). The interim analysis will be performed when 44 out of the expected 87 events have been observed. Using O'Brien-Fleming test boundaries, the Z-score test cut-off at the interim analysis for stopping and rejecting the null hypothesis will be 2.054, the Z-score test cut-off at the interim analysis for stopping and rejecting the alternative (futility) is -0.203.

In order to obtain 94 patients for randomization, we estimate that 25% of patients (24) will undergo progression of disease during induction chemotherapy based on the first 6 months of patient enrollment. In addition, we anticipate that 20% of patients (19) will refuse randomization after up-front systemic therapy. Therefore, in order to randomize 94 patients, we anticipate that we will need to enroll $94 + 24 + 19 = 137$ patients. Note that patients who cross-over to the alternative treatment arm due to toxicity will be censored at the time of crossover, with the last progression-free date being the date of crossover.

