7.5 Statistical Analysis Plan

Descriptive statistics will be provided to summarize the patient characteristics and toxicities by the treatment arms (immediate LCT and delayed/no LCT groups). Chi-square test or Fisher's exact test will be applied to compare patient characteristics between the two arms. The balance of the five prognostic covariates (used in the Pocock-Simon's dynamic allocation method) between the two arms will be examined as well. For the primary endpoint, PFS, Kaplan-Meier estimate will be computed, and the log-rank test will be performed to compare the difference of PFS between the two arms. Cox regression model will be applied to correlate PFS with potential covariates in both the univariate and multi-covariate analyses. Patients are considered evaluable for efficacy if they receive at least one of the intended local consolidation therapy. Both the intent-to-treat analysis and analysis among the evaluable patients will be performed. The corresponding results will be compared and contrasted. For the secondary endpoints, similar analysis will be performed on the overall survival and other time-to-event endpoints. Safety and tolerability of the immediate LCT arm and delayed/no LCT arm will be summarized by descriptive statistics. Quality of life will be analyzed by the repeated measures analysis of variance to count for the change before and after treatment and during the follow-up period. Proper transformation will be performed if necessary to transform data to be closer to the Gaussian distribution. All the statistical analyses will be two-sided with a P-value of 0.10 or less considering statistically significant.

Note that the MDACC DSMB will be providing study-wide oversight in regards to the endpoints described above.

To account for patients that crossover for reasons other than RECIST progression of disease (e.g. toxicity, growth of the malignancy that does not constitute RECIST progression), censoring will occur at the time of crossover for our primary analysis. In addition, a secondary time varying covariate Cox model analysis will be done to assess the impact of crossover without RECIST progression.

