7.6 Off-study criteria

Patients who enroll on Step 1 will be followed for survival status prior to step 2 if they: 1) progress on chemotherapy, 2) experience toxicity that is deemed to be unacceptable by the treating physician prior to the minimum requirements for induction chemotherapy (i.e. 4 cycles of platinum doublet therapy, 3 months of erlotinib/ afatinib, or 3 months of crizotinib), or 3) refuse randomization. If this occurs, they will remain on study only until proceeding to LCT at the end of induction chemotherapy, if applicable (e.g. without any maintenance therapy or second line systemic therapy), and will be followed for survival status at the conclusion of LCT. Allowing patients to remain on study until the time of LCT will allow for tissue collection if the patient proceeds to surgical resection. Patients who do not proceed with randomization but do not proceed immediately to LCT (receiving maintenance therapy or further systemic therapy) will be followed for survival status immediately after proceeding to maintenance therapy or further systemic therapy.

Patients who continue to step 2, or enroll at step 2, will be followed for survival status at the time of RECIST progression. Patients that are randomized to the immediate LCT arm will be followed for survival status immediately after experiencing RECIST progression. Patients that are randomized to the delayed LCT arm that experience progression will remain on study until the completion of LCT *only if LCT is planned within 6 weeks*. In this scenario, the patient will be followed for survival status at the conclusion of LCT. If no LCT is planned within this timeframe (i.e. if second line chemotherapy is planned and not LCT), the patient will be followed for survival status immediately after experiencing RECIST progression. Allowing patients to remain on study until the time of LCT will allow for tissue collection at that time if the patient proceeds to surgical resection. At that time, crossover can occur between treatment arms, at the treating physician's discretion. Crossover can also occur due to treatment toxicity or an increase in the size of disease that does not meet the criteria of RECIST progression. Patients who do not meet the criteria for RECIST progression and crossover to the alternate arm (e.g., crossover for a reason other than progression) will remain on study and will be followed for survival status.

8. Evaluation of Outcomes of Interest

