Appendix A. Timeline of evaluations before, during and after randomization.

Study Test	Baseline (prior to randomizati on)	After randomizat ion, prior to treatment – Treatment= 0 weeks	8 weeks +/- 2 weeks	16 weeks +/- 2 weeks	24 weeks +/- 2 weeks	32 weeks +/- 2 weeks	40 weeks +/- 2 weeks	48 weeks +/- 2 weeks
PET/CT or CT Scan Chest	X (PET/CT scan preferred)		X	X	X	X	X	X
MRI Brain or CT Head	X (all patients, MRI Brain preferred)		X (if brain mets)	X (if brain mets)	X (if brain mets)	X (if brain mets)	X (if brain mets)	X (if brain mets)
Blood-Based Biomarkers (optional study)		X	X	X	X	X	X	X
Toxicity Assessment		X	X	X	X	X	X	X
Quality of Life Symptom Assessment (optional study)		X	X	X	X	X	X	X

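### Quality of life is assigned to repeated-measures ANOVA although symptom forms in effect end at progression; in its classical form that method would use only about a quarter of patients

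*Combined protocol and SAP*

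**What the plan says.** Quality of life is a secondary objective (Section 1.2), and Section 5B makes symptom severity and interference over time a secondary endpoint. The whole analysis plan for it is one sentence in Section 7.5, plus a remark on transformation towards normality: "Quality of life will be analyzed by the repeated measures analysis of variance". The stated aim is to capture pre- to post-treatment change and the later course. No covariance structure, missing-form rule or likelihood-based alternative is given.

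Four other places fix how much data there will be:

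- **Schedule.** Appendix A lists seven symptom assessments: one after randomization and before treatment (week 0), then weeks 8, 16, 24, 32, 40 and 48. The row is marked as optional.
- **Collection.** Section 5B says "this data will be collected from each patient at each follow-up visit".
- **End of follow-up.** Section 4.0 says "All patients will be followed until progression of disease is documented or two years after randomization, whichever comes first".
- **After progression.** Section 7.6 says randomized patients "will be followed for survival status at the time of RECIST progression". There are two exceptions. Delayed-arm patients with LCT planned within 6 weeks stay on study until LCT is completed. Patients who cross over without RECIST progression remain on study.

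No sentence says outright that MDASI-LC forms stop at progression. It follows from reading Sections 4.0, 5B and 7.6 together.

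**The concern.** Classical repeated-measures ANOVA needs a complete set of visits for each patient and drops anyone with a gap. Here the later forms are missing by design, and what removes them is the primary outcome. Under the plan's alternative hypothesis progression comes sooner in the delayed/no LCT arm, so that arm loses more forms. A complete-series analysis would therefore rest on a small group selected by PFS, and selected at different rates in the two arms. What is at stake is the precision of the quality-of-life comparison and whether the reported symptom course describes the randomized patients or mainly those who stayed progression-free.

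**Working it through.** **Inputs.** Section 7.4: "Median PFS equals to 4 months in the delayed/no LCT group and equals to 7 months in the immediate LCT group"; 94 patients randomized over 37.6 months plus 9 months of follow-up; 87 expected events. Section 4.0: 1:1 allocation, so 47 per arm. Appendix A: forms at weeks 0 to 48. Exponential PFS is my assumption.

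**Step 1: reproduce the plan's own figure.** The documents give no quality-of-life number, so I tested the PFS assumptions on the 87 events. With hazard λ = ln 2 / median, accrual A = 37.6 and follow-up F = 9, the expected event share is 1 − [exp(−λF) − exp(−λ(A+F))] / (λA).

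- Median 4: λ = 0.1733; share = 1 − (0.2102 − 0.0003)/6.516 = 0.968; × 47 = 45.5.
- Median 7: λ = 0.0990; share = 1 − (0.4102 − 0.0099)/3.723 = 0.892; × 47 = 41.9.
- Total 87.4, which matches 87. The exponential assumption is consistent with the plan.

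**Step 2: share still progression-free at each form.** The share is 2^(−t/median), with t in months = weeks × 12/52.18.

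| Week | Months | Delayed/no LCT | Immediate LCT | Average | Of 94 |
|---|---|---|---|---|---|
| 8 | 1.84 | 72.7% | 83.3% | 78.0% | 73.3 |
| 16 | 3.68 | 52.9% | 69.5% | 61.2% | 57.5 |
| 24 | 5.52 | 38.4% | 57.9% | 48.2% | 45.3 |
| 32 | 7.36 | 27.9% | 48.3% | 38.1% | 35.8 |
| 40 | 9.20 | 20.3% | 40.2% | 30.3% | 28.4 |
| 48 | 11.04 | 14.8% | 33.5% | 24.1% | 22.7 |

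A complete series needs progression-freedom to week 48: 6.9 of 47 and 15.8 of 47, about 23 of 94. Over all seven forms, including week 0 at 100%, the average observed share is 54%.

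**Step 3: vary the assumptions.**

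- Form still taken at the visit where progression is found (progression-free to week 40 suffices): 28 of 94.
- Last visit anywhere in weeks 46 to 50: 25.5% to 22.8%.
- Median of 4 months in both arms (the null): 14 of 94.
- Assumed uptake of 80% or 60% of this optional assessment: 22.7 × 0.8 = 18, or 22.7 × 0.6 = 14.
- For half the patients to be complete, median PFS would have to be about 11 months.

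**Step 4: consequence for the estimate.** This is a simulation in which every symptom parameter is assumed, because the documents give none: seven visits, random intercept SD 1.5, random slope SD 0.15 per visit, residual SD 1, a true change of 0.90 in both arms, and dropout at progression with log-hazard 0, 0.3 or 0.5 per point of the last score. Ranges cover runs of at least 1,500 trials that differ in coding details.

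| Week-48 quantity | Complete series | All available forms |
|---|---|---|
| SD of arm difference in change | 0.79–0.81 | 0.64–0.68 |
| Mean within-arm change when symptoms predict progression (true 0.90) | 0.75–0.85 | 0.88–0.90 |
| Mean arm difference, complete series (true 0) | 0.00–0.06 | – |

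Using all forms lowers the variance by 1 − (0.68/0.81)² = 30% to 1 − (0.64/0.79)² = 34%. The 0.64 is slightly optimistic because it treats the covariance as known. The arm-difference bias of at most 0.06 is small against an SD of about 0.8.

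**The case against.** The strongest reply is that the plan never states listwise deletion, a complete-series requirement, or one model across all seven visits. Its wording also fits a simple before-and-after contrast, or a likelihood-based fit that goes by the same name. A week-0 to week-8 contrast would keep about 78% of patients even with complete cases. This stands: a reader might infer that the plan discards most of its data, but the documents do not say so. It does not remove the point, since the only named method, in its classical form, has this property and nothing in Section 7.5 excludes that form.

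A reader might also take 23 of 94 as a ceiling. It is not. It is an expected count under exponential PFS, scans and forms share the 8-week schedule so a form may be completed at the progression visit, and the Section 7.6 exceptions can add a few more. The share remains a minority.

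A third tempting inference is that the randomized comparison is broken. Completion does differ by arm (33.5/14.8 = 2.3-fold), but in the simulation both arms shifted in the same direction and the arm difference was close to unbiased. A true arm difference in symptoms was not simulated.

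Finally, the simulation favours the remedy. Dropout depends on the last observed score, which is the missing-at-random condition under which a mixed model is valid, and no not-at-random case was run. That is a fair limit on how much the mixed model can be said to repair.

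**Conclusion.** The point holds in a limited form. The named method fits poorly with forms that in effect end at progression. Applied classically, it would rest on about 23 to 28 of 94 patients before optional uptake is considered. On that reading the likely harms are an arm comparison with a variance that could be cut by about 30% or more, and an understated worsening within each arm when symptoms predict progression. The patient counts rest on the plan's medians and exponential PFS; the size of the harms rests on assumed symptom parameters. Neither complete-case analysis as the plan's stated intent nor a materially biased arm difference is supported. The endpoint is secondary and optional, and the primary PFS analysis is not touched, so this is a worthwhile correction and not a threat to the trial's main result.

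**What to change.** In Section 7.5, replace the ANOVA with a linear mixed model for repeated measures on all available MDASI-LC scores:

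- **Terms:** arm, visit, arm-by-visit and the week-0 score. Keep other covariates sparse: with about 7 delayed-arm forms expected at week 48, adding all five minimization factors to an unstructured covariance may not be estimable.
- **Covariance:** unstructured, with a pre-specified simpler fallback (for example random intercept and slope) if it does not converge.
- **Main contrast:** an early visit where most patients still contribute, for example week 8 (about 73 of 94 at full uptake) or week 16 (about 57 of 94).
- **Interpretation:** state the missing-at-random assumption, and that late-visit contrasts extrapolate to patients who have already progressed. The week-48 contrast should not be labelled as symptom burden up to progression.
- **Reporting:** number of patients contributing at each visit, by arm.
- **Collection:** say in Section 5B or 7.6 whether a form is taken at the progression visit and whether collection stops there.

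The cost is a paragraph of SAP wording and standard software, with no added visits or patients. The downsides are reliance on missing-at-random, which cannot be verified from the data, and a main contrast that speaks only to early symptom burden.

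### The quality-of-life analysis in section 7.5 names no between-arm contrast and no baseline adjustment; read literally it tests change over time, and the default arm terms can use the data less well than a baseline-adjusted comparison

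*Combined protocol and SAP*

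**What the plan says.** Section 1.2 lists quality of life among the secondary objectives, and section 5(B) makes MDASI-LC symptom severity and interference over time a secondary endpoint. The analysis is one sentence in section 7.5: "Quality of life will be analyzed by the repeated measures analysis of variance to count for the change before and after treatment", extended to the follow-up period. A further sentence allows transformation towards normality. The section does not name the arm term, an arm-by-visit term, a baseline covariate, a primary score or visit, or a covariance structure.

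The significance rule is general: "All the statistical analyses will be two-sided with a P-value of 0.10 or less considering statistically significant".

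Appendix A has a row labelled "Quality of Life Symptom Assessment (optional study", with one score after randomization but before treatment (week 0) and six more at weeks 8, 16, 24, 32, 40 and 48. The column before randomization is empty for this row. Section 1.3 describes the trial as open-label.

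**The concern.** The other outcomes in section 7.5 are tied to the arms. PFS gets a log-rank comparison of the two arms, overall survival and the other time-to-event endpoints are handled in the same way, and toxicity is summarized for each arm. Quality of life is tied only to movement in the score across the pre-treatment, post-treatment and follow-up periods. In a repeated-measures ANOVA that is the time effect, whose null hypothesis is no change over visits. Rejecting it says nothing about whether local consolidation therapy (LCT) changes symptoms relative to delayed or no LCT.

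An analyst who wants an arm comparison must choose a term that the plan does not name: the arm main effect, arm-by-time, or a comparison of change scores. The choice could be made after seeing open-label data, and these tests differ a good deal in power. A real effect on symptoms could be missed, or a general change over time could be read as a treatment finding.

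**Working it through.** **Inputs from the documents.** Section 4.0 has patients "randomized in a 1:1 fashion to either immediate or no/delayed LCT", and section 7.4 says "this design would require 94 patients *randomized* over 37.6 months with additional 9 months of follow-up". So 94/2 = 47 per arm, an upper bound here because the questionnaire is optional. Quality of life is tested two-sided at 0.10. There are seven scores: one at week 0 and six in follow-up.

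**The plan's own figure.** No power is stated for quality of life, so the only figure to reproduce is the PFS size. Section 7.4 sets it by "A design with one-sided 10% type I error and 90% power" and arrives at 87 events. With "Median PFS equals to 4 months in the delayed/no LCT group and equals to 7 months in the immediate LCT group", a fixed design needs 4 x (1.2816 + 1.2816)^2 / (ln 1.75)^2 = 83.9, that is 84 events. Adding the single interim look with the stated boundaries gives 86.5, that is 87. Uniform accrual of 94 patients over 37.6 months plus 9 months of follow-up gives 87.4 expected events. The 94 is sound as an input.

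**Assumptions, not in the documents.** SD 1 at every visit; a constant post-baseline arm difference of 0.4; complete data; exchangeable correlation r of 0.5, 0.6 or 0.7, or first-order autoregressive correlation of 0.7 or 0.8.

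**Formulas, with r = 0.6 exchangeable.** The standard error is sqrt(V x 2/47).

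- Follow-up mean adjusted for week 0: V = (1 + 5r)/6 - r^2 = 0.6667 - 0.36 = 0.3067; SE 0.1142; 0.4/0.1142 = 3.50; power 97%.
- Arm main effect over all seven scores: the effect is diluted to 0.4 x 6/7 = 0.3429; V = (1 + 6r)/7 = 0.6571; SE 0.1672; ratio 2.05; power 65%.
- Follow-up mean minus week 0: V = (1 + 5r)/6 + 1 - 2r = 0.4667; SE 0.1409; ratio 2.84; power 88%.
- Arm-by-time: noncentrality = (47/2) x 0.4^2 x (6/7)/(1 - r) = 23.5 x 0.1371/0.4 = 8.06, on 6 and 6 x 92 = 552 degrees of freedom; power 65%.

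Under autoregressive correlation the same quantities come from the full covariance matrix. For arm-by-time, the degrees of freedom and the noncentrality are multiplied by the Greenhouse-Geisser factor (0.58 and 0.51).

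| Correlation | Adjusted follow-up mean | Arm main effect | Arm-by-time | Follow-up minus week 0 |
|---|---|---|---|---|
| Exchangeable 0.5 | 95% | 71% | 56% | 81% |
| Exchangeable 0.6 | 97% | 65% | 65% | 88% |
| Exchangeable 0.7 | 98% | 61% | 78% | 95% |
| Autoregressive 0.7 | 89% | 74% | 40% | 66% |
| Autoregressive 0.8 | 90% | 66% | 47% | 75% |

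Simulation of complete trials with an estimated Greenhouse-Geisser correction agrees within a few points; its arm-by-time range is 36-76%.

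**The time effect.** With identical arms that both shift by 0.3 SD after week 0, the exchangeable 0.6 case has noncentrality 94 x 0.3^2 x (6/7)/0.4 = 18.1 and power 95%. Across the five settings the time test rejects in 74-99% of simulated trials, although the arms do not differ.

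**Effect shape.** Keep the average at 0.4 SD but let the difference fall linearly from 0.8 to 0 over the six visits. Arm-by-time power becomes 93-100%, against an unchanged 89-98% for the adjusted mean. An effect that builds up gives similar results.

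**The case against.** The strongest reply is that the criticised model is partly inferred. The sentence in section 7.5 does not say that the week-0 score is one of the outcomes, nor which term is tested. It could mean change from baseline compared between arms, which suits a trial whose stated purpose is an arm comparison. This stands: the plan is silent, and no particular flawed test can be attributed to it. What remains is that the arm contrast and the baseline adjustment are not specified.

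Four stronger readings are tempting, and the documents do not support them.

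- A reader might infer that the arm tests usually lose 20 or more points of power. That depends on the test, the correlation and the effect shape. The change contrast loses only about 3-23 points in the table, below 20 in four of five settings. The main effect loses 15 under autoregressive 0.7. With a fading effect, arm-by-time loses nothing.
- The 74-99% rejection rate might be taken for an inflated error rate. It is not: a change was simulated, so the time test correctly rejects its own null. The point is only that this null is not the trial's question.
- Having the week-0 score among the outcomes might be blamed for the loss. A longitudinal model that does so but gives both arms a common baseline mean loses no power. The loss comes from leaving that mean free and testing the default terms.
- The remedy might be taken to be wording alone. That is true of the contrast, but not of a baseline score taken without knowledge of the arm, which is not scheduled.

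Materiality is also limited. The questionnaire is optional, and section 7.6 moves patients to survival follow-up around RECIST progression. On the design medians about 7 of 47 and 16 of 47 would be progression-free at week 48, so the complete-data powers compare methods and do not forecast this trial's power.

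**Conclusion.** The concern holds in a limited form. The single quality-of-life sentence points to change over time, and names neither the between-arm contrast nor a baseline adjustment that the objective calls for. With a constant 0.4 SD effect and the stated correlations, the baseline-adjusted follow-up mean has 89-98% power. It exceeds the arm main effect (61-74%), arm-by-time (about 40-78%) and the change contrast (66-95%) in every setting tried. These gaps rest on complete data, 47 per arm and a constant effect, none of which the documents assure for this endpoint; under a fading or building effect the ranking against arm-by-time can reverse. The matter concerns a secondary, optional endpoint and should be corrected, but it does not touch the primary PFS conclusion.

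**What to change.** In section 7.5, define the main quality-of-life comparison as the between-arm difference in post-baseline MDASI-LC severity and interference, averaged over the scheduled follow-up visits. Estimate it in a longitudinal mixed model with arm, visit, arm-by-visit and the week-0 score as a covariate, or equivalently in a model with the week-0 score among the outcomes and a common baseline mean across arms. Keep arm-by-visit as a supporting test for effects that vary over time, and report within-arm change descriptively.

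This part costs only SAP wording and uses scores already scheduled. Its downside is that an averaged contrast is less sensitive to effects that change over time, which is why the supporting test should stay.

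A separate decision is needed on the baseline score. Appendix A places it after randomization in an open-label trial, so answers may reflect knowledge of the assigned arm. Avoiding that means moving the first questionnaire to before randomization, which is a change to the assessment schedule as well as to the SAP.

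### The secondary crossover model in 7.5 is open to confounding by indication: tumour growth short of RECIST progression can trigger crossover and plausibly precedes progression

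*Combined protocol and SAP*

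**What the plan says.** Section 7.5 handles crossover without RECIST progression in two ways. For these patients, "censoring will occur at the time of crossover for our primary analysis". The section then promises a further model, in these words: "a secondary time varying covariate Cox model analysis will be done to assess the impact of crossover without RECIST progression". The reasons are given as examples: "e.g. toxicity, growth of the malignancy that does not constitute RECIST progression". Section 7.6 repeats them as a rule: "Crossover can also occur due to treatment toxicity or an increase in the size of disease that does not meet the criteria of RECIST progression". The study schema leaves crossover to the treating physician's discretion.

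The sentence on the secondary model gives no endpoint, no covariates and no coding of crossover. Elsewhere 7.5 says that a "Cox regression model will be applied to correlate PFS with potential covariates in both the univariate and multi-covariate analyses", but the covariates are unnamed and nothing measured on study is mentioned. No weighting or structural method is named.

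On follow-up, 7.6 says that patients who cross over without RECIST progression "will remain on study and will be followed for survival status". Section 8 asks for imaging about every 8 weeks after randomisation, whatever treatment the patient is receiving.

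**The concern.** A time-varying crossover term compares the hazard of patients after crossover with that of patients still at risk who have not crossed. Coding crossover as time-varying removes immortal-time bias. It does not make the two groups alike at the moment of crossover. A patient who crosses because of "an increase in the size of disease that does not meet the criteria of RECIST progression" is plausibly closer to RECIST progression than the average patient who has not crossed. The hazards would then differ even with a null treatment effect, and the coefficient would answer a question about prognosis rather than about impact.

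This is the only analysis in the plan aimed at crossover, and it concerns the same patients whom the primary analysis censors. In the delayed arm, crossover means receiving LCT, so a spurious hazard ratio above 1 could be read as harm from the treatment under test. The threshold for all analyses in 7.5 is two-sided 0.10, which makes such a finding easier to declare.

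**Working it through.** **The plan's own figure.** The documents give no number for the crossover model, so the check starts from the design in 7.4: medians of 4 and 7 months (HR 4/7 = 0.571), one-sided 10% error, 90% power, 94 patients over 37.6 months plus 9 months of follow-up, and 87 events.
- Fixed-design events (Schoenfeld): 4 × (1.2816 + 1.2816)² / (ln 1.75)² = 4 × 6.570 / 0.3132 = 83.9, so 84.
- With the stated interim cut-offs (2.054 and −0.203 at 44 of 87 events) and an overall one-sided 10%, power at 87 events is 0.9015.
- Expected events under exponential PFS are 47 × [1 − (e^(−9λ) − e^(−46.6λ)) / (37.6λ)] per arm, with λ = ln 2/4 and ln 2/7. This gives 45.5 + 41.9 = 87.4.

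The design figure reproduces, so these inputs are a fair base.

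**Why the coefficient moves.** Let growth multiply the progression hazard by k. At a given time within an arm, let p1 be the share of crossed-over patients who are growing, and p0 the share of those not crossed. If crossover does nothing, the hazard ratio is

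HR = [1 + p1(k − 1)] / [1 + p0(k − 1)].

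It equals 1 if k = 1 or p1 = p0. It exceeds 1 whenever k > 1 and p1 > p0, and reaches k only if p1 = 1 and p0 = 0. Toxicity crossovers lower p1, and growing patients who stay on their arm raise p0. Both dilute the bias.

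**Simulation 1.** 94 patients, the 7.4 medians, growth detected at 8-weekly scans, progression follow-up capped at 24 months (Section 4.0), full RECIST follow-up after crossover, true crossover HR exactly 1. The model held arm and time-varying crossover. Assumed: k, the share of growing patients who cross, and the toxicity rate. The nominal rate of significant harm is 5% (two-sided 0.10). With half of growing patients crossing (600 trials per cell):

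| k | Growth crossovers only | About half for toxicity | Toxicity only |
|---|---|---|---|
| 1 | HR 1.03, harm 5% | HR 0.99, harm 6% | HR 1.00, harm 7% |
| 2 | HR 1.53, harm 44% | HR 1.30, harm 29% | HR 0.99, harm 5% |
| 4 | HR 2.75, harm 91% | HR 1.60, harm 56% | HR 1.01, harm 6% |

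Adding true growth status as a time-varying covariate gave HR 0.99 to 1.03 and harm in 5 to 7% throughout.

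With 15% of growing patients crossing and k from 1.5 to 4 (800 trials per cell):
- about 5 to 6 growth crossovers, none for toxicity: HR 1.28 to 2.61, harm 16 to 53%;
- about 10 to 11 crossovers, roughly half for growth: HR 1.12 to 1.41, harm 13 to 27%;
- about 20 crossovers, 4 to 5 for growth: HR 1.06 to 1.19, harm 8 to 16%.

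**Simulation 2, with explicit tumour measurements.** Assumed: half of progressions preceded by 2 to 6 months of measurable growth, crossover possible at a scan showing 10 to 19.9% growth, toxicity crossover 0.3% per month, 200 trials per scenario. With on average 4, 6, 9 and 15 crossovers, the null crossover term was significant in 25%, 46%, 70% and 95% of trials against a nominal 10% (median HR 1.8, 2.1, 2.4, 2.8). With toxicity crossovers only it was 9%.

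**Which adjustment works.** LCT changes later measurements, so the choice of scan matters.
- Adjusting for the most recent scan, when crossover treatment shrinks measured disease (assumed to −20%), moved a null effect from HR 1.54 to 2.05 and harm from 31% to 64%. It turned a true HR of 0.5 into 1.24. A separate run with shrinkage gave HR 1.48 and harm in 38% under a null effect.
- Holding tumour change at the last scan before crossover gave HR 1.05 to 1.16 and harm in 3 to 10% with growth crossovers. A true HR of 0.5 was estimated as 0.53.

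**The case against.** A reader might infer that the model sets growing tumours against non-growing ones and so will report harm. The documents do not support that. Toxicity is named beside growth in both sections, and because crossover is discretionary, patients with growth may also stay on their assigned arm. The bias is a tendency, and it can be small.

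The plan also does not commit to a single unadjusted indicator, or even to PFS as the endpoint. One could read the sentence as a sensitivity check on the censoring, with the arm effect as the quantity of interest. That is fair as to intent. However, the stated purpose is the impact of crossover, and nothing named in the plan would remove the confounding.

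The strongest objection concerns follow-up. If progression is not assessed after crossover, the bias can reverse. With about 13 crossovers, k = 3, a null effect and only a quarter of post-crossover events observed (assumed), the crossover HR was 0.37, with significant benefit in 72% of 200 trials and harm in none. With full follow-up it was 1.61, with harm in 38%. Section 8 points to continued scanning, but 7.6 uses the language of survival follow-up for patients after RECIST progression as well as for these patients. This objection stands as a condition on the direction.

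**Conclusion.** The concern holds as a weakness of a secondary analysis. As written, the model cannot separate the effect of crossover from the prognosis of those who cross, and with continued RECIST assessment it leans towards apparent harm. Over the assumed ranges the null effect appears as a hazard ratio of about 1.06 to 2.8. There is no bias if all crossovers are for toxicity unrelated to prognosis, or if growth does not predict progression. Crossover counts, the growth and toxicity mix, and the strength of growth as a predictor are all assumptions, because the documents give none of them.

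A reader might also infer that the primary result is compromised through this model. The documents do not support that: the primary comparison is the log-rank test with censoring at crossover, and no section lets this coefficient correct it or drive a decision. The risk is misinterpretation of a secondary result, and it is worth removing before the data are seen.

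**What to change.** Amend 7.5 as follows:

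1. Record the reason for each crossover without RECIST progression. Report toxicity and growth crossovers as separate time-varying terms, with randomised arm in the model. If either group is too small to fit, report it descriptively only.
2. Adjust for percent change in the sum of diameters, updated at each scan until crossover and then held at the last scan before crossover. Inverse-probability weights built from pre-crossover scans are an alternative. Do not use the most recent scan after crossover.
3. State that the endpoint is PFS and that the 8-weekly imaging of Section 8 continues after crossover without RECIST progression, and reconcile the follow-up wording of 7.6 with this.
4. State that the unadjusted crossover coefficient is a prognostic association and will not be reported as the impact of crossover.

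The cost is SAP wording, one recorded reason and one variable derived from scans that Section 8 already calls for. The downsides are wide intervals and possibly unstable fits if crossovers are few, and some residual confounding because growth between 8-weekly scans is not seen.
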